- 2.1.1.9 At the time of registration: Patients must have recovered from the toxic effects of prior therapy: > 28 days from any investigational agent, > 28 days from prior cytotoxic therapy, > 14 days from vincristine, > 42 days from nitrosoureas, > 21 days from procarbazine administration, > 21 days from bevacizumab administration and > 7 days for non-cytotoxic agents, e.g., interferon, tamoxifen, thalidomide, cis-retinoic acid, etc. (radiosensitizer does not count). Any questions related to the definition of non-cytotoxic agents should be directed to Academic PI.
- 2.1.1.10 Patients must have adequate organ function:
- Bone marrow function (WBC $\geq 3,000/\mu l$, ANC $\geq 1,500/mm^3$, platelet count of $\geq 100,000/mm^3$, and hemoglobin $\geq 10 \text{ gm/dl}$).
 - o Eligibility level for hemoglobin may be reached by transfusion.
- Liver function (alanine amino transferase (ALT) and aspartate aminotransferase (AST) < 2.5 X ULN, and total bilirubin < 1.5 X ULN), prothrombin time (PT) or international normalized ratio (INR), and activated partial thromboplastin time (aPTT) ≤ 1.2 X ULN.

Version Date: 07/17/2025 Page 14 of 96

• Concomitant elevations in bilirubin and AST/ALT above 1.0 x ULN (upper limit of normal) are not permitted.

- O Subjects receiving anticoagulant therapy are eligible if their INR is stable and within the recommended range for the desired level of anticoagulation.
- Renal function (creatinine ≤1.5 mg/dL (133 μmol/L), or if > 1.5 mg/dL, calculated creatinine clearance ≥ 50 cc/min), and urine protein to creatinine ratio of < 1 prior to registration.
 - 2.1.1.11 Patients must have shown unequivocal radiographic evidence for tumor progression by MRI or CT scan as defined by Section 6.4.1.4.5. A scan should be performed within 14 days prior to registration and on a steroid dose that has been stable or decreasing for at least 5 days. If the steroid dose is increased between the date of imaging and registration a new baseline MR/CT is required. The same type of scan, i.e., MRI or CT must be used throughout the period of protocol treatment for tumor measurement.
 - 2.1.1.12 Patients having undergone recent resection of recurrent or progressive tumor will be eligible as long as all of the following conditions apply:
 - They have recovered from the effects of surgery and be > 28 days from surgery.

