3.4 ON STUDY EVALUATION

3.4.1 General Requirements

- 3.4.1.1 CBC with differential and platelets and serum chemistries and LFTs (ALT, AST and bilirubin) will be performed every two weeks X 2, (+/- 3 days) then every 4 weeks (+/- 3 days) prior to each cycle during treatment. UPC (+/- 3 days) will be done monthly prior to each cycle.
- 3.4.1.2 A brain MRI/CT for group B will be done monthly until 3 months then every other month thereafter, for group A scan will be obtained every other month prior to initiation of odd numbered 28 days treatment cycles (+/- 3 days).
- 3.4.1.3 All relevant information regarding drug doses, concomitant medications, and doses, measurable lesions with measurements, tumor response, laboratory examinations, and treatment-related toxicities shall be documented in the patient's medical record and flow sheets.
- 3.4.2 A complete Neurologic exam (to include documentation of the patients Karnofsky Performance Status) will be performed prior to every evaluation where an MRI is scheduled. The MDASI-BT (Appendix 15.5) will be completed at baseline and at the time of each evaluation that includes an imaging study.
- 3.4.3 The patient will complete the MDASI-BT (see Appendix 15.5) at the time of clinical evaluation with MRI as long as the clinical therapy is being administered, unless clinical deterioration makes self-report not possible before that time. The time when patients are unable to complete the self-report questionnaires will be used as part of the study analysis. The MDASI-BT will be completed only by the patient, unless changes in vision

Version Date: 07/17/2025 Page 27 of 96

or weakness make this difficult. If this occurs, then the caregiver or research assistant may read the questions to the patient or assist with marking the severity number or score as described by the patient. A patient caregiver may complete the questionnaires as a patient-preference proxy if the patient's deficits preclude self-report.

- 3.4.3.1 A measurement of BP should be taken twice weekly for the first 2 months of therapy, then weekly for 2 months, and then once per month thereafter as detailed in 3.3.5.2. BP can be assessed by any method (i.e., at home or by another physician) as long as the treating physician is informed of the measurement, verifies any measurement that is not normal and takes appropriate action.
- 3.4.3.2 Thyroid function test (T4 and TSH) (+/- 3 days) are to be monitored every 8 weeks (+/- 3 days)

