6.4.1 Definitions of Response

- 6.4.1.1 Measurable Disease: Bidimensionally measurable lesions with clearly defined margins by CT or MRI scan.
- 6.4.1.2 Evaluable Disease: Unidimensionally measurable lesions, masses with margins not clearly defined.
- 6.4.1.3 Non-Evaluable Disease: Not Applicable for response evaluation
- 6.4.1.4 Objective Status, To Be Recorded at Each Evaluation: If there are too many measurable lesions to measure at each evaluation, choose the largest two to be followed before a patient is entered on study. The remaining lesions will be considered evaluable for the purpose of objective status determination. Unless progression is observed, objective status can only be determined when ALL measurable and evaluable sites and lesions are assessed.
 - 6.4.1.4.1 Complete Response (CR): Complete disappearance of all measurable and evaluable disease. No new lesions. No evidence of non-evaluable disease. All measurable, evaluable and non-evaluable lesions and sites must be assessed using the same techniques as baseline. Patients must be on no steroids.
 - 6.4.1.4.2 Partial Response (PR): Greater than or equal to 50% decrease under baseline in the sum of products of perpendicular diameters of all measurable lesions. No progression of evaluable disease. No new lesions. All measurable and evaluable lesions and sites must be assessed using the same techniques as baseline. The steroid dose at the time of the scan evaluation should be no greater than the maximum dose used in the first 8 weeks from initiation of therapy.
 - 6.4.1.4.3 Partial Response, Non-Measurable (PRNM): Not applicable.
 - 6.4.1.4.4 Stable/No Response: Does not qualify for CR, PR, or progression. All measurable and evaluable sites must be assessed using the same techniques as baseline. The steroid dose at the time of the scan

Version Date: 07/17/2025 Page 36 of 96

evaluation should be no greater than the maximum dose used in the first 8 weeks from initiation of therapy.

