- 6.4.1.4.5 Progression: 25% increase in the sum of products of all measurable lesions over smallest sum observed (over baseline if no decrease) using the same techniques as baseline, OR clear worsening of any evaluable disease, OR appearance of any new lesion/site, OR clear clinical worsening or failure to return for evaluation due to death or deteriorating condition (unless clearly unrelated to this cancer). Patients will also be considered to have progressive disease if there is significant increase in T2/FLAIR non-enhancing lesions AND clinical progression. (See section 6.4.1 and 6.3.7 for definitions). To be considered progressive disease, increase in T2/FLAIR should occur on stable or increasing doses of corticosteroids compared to baseline scan or best response following initiation of therapy, and should not be due to co-morbid events (e.g. radiation therapy, demyelination, ischemic injury, infection, seizures, post-operative changes, or other treatment effects).
- 6.4.1.4.6 Unknown: Progression has not been documented and one or more measurable or evaluable sites have not been assessed.
- 6.4.2 Best Response: This will be calculated from the sequence of objective statuses.

For patients with all disease sites assessed every evaluation period, the best response will be defined as the best objective status as measured according to Section 6.4.1. If the response does not persist at the next regular scheduled MRI, the response will still be recorded based on the prior scan, but will be designated as a non-sustained response. If the response is sustained, e. g. still present on the subsequent MRI, it will be recorded as a sustained response, lasting until the time of tumor progression. Best response is unknown if the patient does not qualify for a best response or increasing disease and if all objective status determinations before progression are unknown.

- 6.4.3 Neurological Exam: Although not used for determining response, it is useful to evaluate improvement in the neurologic exam, (as compared to the baseline assessment), that should coincide with objective measurement of tumor size.
 - +1 Better
 - 0 Unchanged
 - -1 Worse
 - B Baseline

Version Date: 07/17/2025 Page 37 of 96

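### The steroid condition for partial response cannot fail at scans up to week 8, so shrinkage after a steroid increase could count as a response

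*Combined protocol and SAP*

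**What the plan says.** Section 6.4.1.4.2 defines PR by the tumor change "Greater than or equal to 50% decrease under baseline in the sum of products of perpendicular diameters of all measurable lesions", with no new lesions and no progression of evaluable disease. It adds that the steroid dose at the scan should be "no greater than the maximum dose used in the first 8 weeks from initiation of therapy". Section 6.4.1.4.4 repeats the same steroid limit for stable disease. Complete response (6.4.1.4.1) is stricter: "Patients must be on no steroids".

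On timing, section 3.4.1.2 states "A brain MRI/CT for group B will be done monthly until 3 months then every other month thereafter". Group A is scanned before each odd-numbered 28-day cycle, with a tolerance of 3 days either way.

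Under 6.4.2, a response that is gone at the next MRI still counts as the best response and is labelled non-sustained. Objective response rate is a secondary endpoint in 1.1.2. Sections 1.1.2 and 9 also compare symptom scores between responders and non-responders.

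**The concern.** A steroid qualifier on response is there to stop a steroid effect on the image from being credited to the study drugs. PR measures shrinkage from the baseline scan, so the natural reference is the dose at that scan. The plan instead uses a maximum taken over a period on treatment. If the dose is raised in that period, the limit rises with it.

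At stake are the objective response rate in both groups and the split into responders and non-responders used for the MDASI-BT analysis. Neither group has a concurrent control, so nothing in the data would show how many responses followed a steroid change. Because 6.4.2 does not require confirmation, one affected scan is enough to set a patient's best response.

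**Working it through.** The plan gives no response-rate figure to reproduce. The check is of the logic of the definition.

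**Inputs**
- Limit: maximum dose over weeks 0 to 8 of therapy (6.4.1.4.2).
- Group B scans: weeks 4, 8 and 12, then every 8 weeks (3.4.1.2; calendar in 3.6).
- Group A scans: before cycles 3, 5 and 7, that is 28 × (3 − 1)/7 = week 8, 28 × (5 − 1)/7 = week 16 and 28 × (7 − 1)/7 = week 24.
- Ceiling: dexamethasone 16 mg/day (4.2).

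**Step 1: scans up to week 8.** Let d(t) be the dose at week t and M = max{d(s): 0 ≤ s ≤ 8}. The condition is d(t) ≤ M. If t ≤ 8, then d(t) is a member of the set whose maximum is M, so d(t) ≤ M always holds. The condition is empty at the nominal week 4 and week 8 scans in Group B and the nominal week 8 scan in Group A.

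**Step 2: later scans.** The condition fails only if d(t) > M. Take an illustrative patient on 2 mg at baseline, raised to 16 mg at week 3 and kept there. Then M = 16 and the condition is met at weeks 4, 8, 12 and every later scan. A comparison with baseline would fail at each of them, since 16 > 2.

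**Step 3: enumeration.** Assume dose levels of 0, 2, 4, 8 and 16 mg at weeks 0, 2, 4, 6, 8, 10 and 12. This gives 5^7 = 78,125 dose paths.

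| Scan week | Dose above week-0 dose | Fails the plan's condition | Above week-0 dose but passes |
|---|---|---|---|
| 4 | 31,250 | 0 | 31,250 |
| 8 | 31,250 | 0 | 31,250 |
| 12 | 31,250 | 6,500 | 24,750 |

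Hand check: 10 of the 25 ordered pairs of levels have the later dose higher, and 10/25 × 78,125 = 31,250 (40%). At week 12 the dose must exceed all five doses from weeks 0 to 8, with week 10 free: 5 × (0^5 + 1^5 + 2^5 + 3^5 + 4^5) = 5 × 1,300 = 6,500. Then 31,250 − 6,500 = 24,750. The shares depend on the assumed grid and do not predict frequencies. The zeros at weeks 4 and 8 do not depend on it.

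**Step 4: does another rule close the gap?**
- Section 2.1.1.11 controls the dose before registration only: "If the steroid dose is increased between the date of imaging and registration a new baseline MR/CT is required".
- Section 4.2 asks for the smallest dose that controls symptoms and sets the ceiling. This bounds an increase but does not rule one out.
- Time to treatment failure (6.4.5) counts a lasting rise in steroid need, but it is not among the endpoints in 1.1.

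No rule for PR compares the dose at the scan with the dose at baseline.

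**Step 5: does the condition reach PFS?** Progression under 6.4.1.4.5 requires growth of 25%, clear worsening of evaluable disease, a new lesion, clinical worsening, death or deterioration, or a T2/FLAIR increase together with clinical progression. Failing the PR or stable-disease steroid condition is not on that list. A non-progressing scan that fails it therefore has no defined status: it is not a response, stable disease or progression, and the unknown category is reserved for sites that were not assessed.

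**The case against.** The strongest case for leaving the text alone is that the gap is narrow. Complete response is protected, PR needs at least a 50% decrease, steroids are to be kept low and are capped, unsustained responses are labelled, and clinical worsening counts as progression whatever the scan shows. The response rate is secondary and carries no test or decision rule. All of this is correct, and it is why the point is minor. These safeguards narrow the gap without closing it, because none compares the dose with baseline.

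The scan counts are also nominal. A week 8 scan may be done up to 3 days late, and Group A scans are tied to cycles that can be delayed for toxicity (3.3.1, 3.3.6.14). A scan after week 8 falls outside the window, and there the condition can fail. That stands.

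One might argue that the T2/FLAIR clause shows baseline to be the protocol's own standard. It does not carry that weight. That change "should occur on stable or increasing doses of corticosteroids compared to baseline scan or best response following initiation of therapy", so its reference can also come after baseline, and it guards against the opposite error of calling progression after a steroid reduction. The case rests on the PR definition itself.

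A reader might go further and infer that the empty condition undermines PFS3, since it covers two of the three Group B scans up to 3 months and a single patient could move the result from 1/32 to 2/32, the threshold for promise. The documents do not support this. By step 5, a patient without a progression event stays progression-free whether the condition is empty, strict or tied to baseline. Steroids might hold measured growth under 25%, but that would be a question about 6.4.1.4.5, and rewording PR would not change it.

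**Conclusion.** The point holds for response classification. The PR steroid condition has no force at any scan done on or before week 8, and an early increase weakens it at all later scans. This is a logical certainty and needs no assumption about steroid use. Whether it matters in practice depends on how many patients have a dose increase followed by a decrease of at least 50% in measured tumor, which the documents do not give. The supportable statement is therefore that the response rate could be inflated and the MDASI-BT responder comparison blurred, by an unknown amount. The conclusion does not extend to PFS3, PFS6 or either two-stage decision rule. Severity: minor.

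**What to change.** - In 6.4.1.4.2, for response classification only, require that the steroid dose at the PR scan be no greater than the dose at the baseline scan.
- In 6.4.1.4.4, state what status a non-progressing scan on a higher steroid dose receives, for example stable disease, so that none is left unclassified.
- If data collection is complete, keep the existing classification and report the response rate under both definitions.

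The cost is two wording changes and one extra tabulation. Concomitant medications and doses are already documented under 3.4.1.3, and eligibility under 2.1.1.11 already depends on the steroid dose around the baseline scan. The response rate may come out slightly lower. Steroid management of patients and the primary endpoint are untouched. I would not add a PFS analysis that treats every dose above baseline as failure: 4.2 permits steroids for edema and mass effect, so it would exchange one misclassification for another. Label: cheap improvement.

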6.4 RESPONSE CRITERIA

The primary efficacy endpoint is progression free survival (PFS) at six months from patient registration for bevacizumab naïve patients and PFS at 3 months for patients with prior bevacizumab treatment. However, objective response status should be measured and recorded.

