6.4.4 Performance Status: Patients will be graded according to Karnofsky Performance Status (See Appendix 15.1). Clinical progression can be declared if there is a decrease in 100 or 90 to 70 or less, at least 20 from 80 or less, or decline in KPS from any baseline to 50 or less, for at least 7 days and not attributable to comorbid events or change in steroid dose.

- 6.4.5 Time to Treatment Failure: From date of registration to the date of first observation of progressive disease (as defined in Section 6.4.1.4.5), non-reversible neurologic progression or permanently increased steroid requirement (applies to stable disease only), death due to any cause, or early discontinuation of treatment.
- 6.4.6 Time to Death: From date of registration to date of death due to any cause.
- 6.4.7 Documenting FLAIR: investigators will be asked to measure tumor related changes on FLAIR sequence as best as possible, as non-enhancing patterns of recurrence can occur. If this occurs within the setting of clinical progression not caused by seizures or other identifiable cause, the patient will be considered to have progressive disease. Please see section 6.4.1 for definition of clinical progression.

Presumed non-enhancing tumor without clinical progression should be observed. The time of progression if eventual clinical deterioration occurs can be back dated to the time of the increase in non-enhancing tumor. Investigators will also be asked to document if recurrence of disease is multifocal.

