9 STATISTICAL CONSIDERATIONS

For this study, since there is experience with the drug combination a formal DSMB review will not be necessary.

Time to progression and overall survival will be evaluated using the Kaplan-Meier product-limit survival curve methodology. Six-month Progression Free Survival (PFS) will be estimated using Kaplan-Meier estimates and associated two-sided 95% confidence intervals.

Recurrent glioblastoma with no prior exposure to bevacizumab cohort (Group A): A maximum of 34 patients will be observed in a two-stage Simon optimum design. In the first stage, 9 patients will be accrued. If two or more patients are progression-free at 6 months (PFS6), an additional 25 patients will be accrued. We halt registering patients after 9 patients until we have at least 2 patients are progression free at six months. If 9 or more out of 34 have PFS6, then the study will be declared promising. This study has a 5% chance of declaring promise if the PFS6 rate is at most 15%. It has an 80% chance of declaring promise if the PFS rate is at least 35%.

Recurrent glioblastoma with prior exposure to bevacizumab cohort (Group B): In the group that failed bevacizumab, a maximum of 32 patients will be observed in a two-stage Simon

Version Date: 07/17/2025 Page 43 of 96

optimum design. In the first stage, 14 patients will be accrued. If one or more patients is progression-free at 3 months (PFS3), an additional 18 patients will be accrued. We will halt registration after 14 patients until at least 1 patient is progression free at 3-months. If 2 or more out of 32 have PFS3, then the study will be declared promising. This study has a 5% chance of declaring promise if the PFS3 rate is at most 1%. It has an 80% chance of declaring promise if the PFS rate is at least 12%.

In both patient cohorts, for patients who drop out for reasons other than PD or toxicity, we will replace them. We expect the dropout rate to be not more than 10%, therefore in general it is not an issue to implement the design. The patients who drop out due to toxicity will be counted as treatment failure when implementing the Simon's two stage design and assessing the 6-month PFS rate in either cohort.

The trial will be monitored by the Academic PI, [name], and the study statistician, [name].

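### PFS, the primary endpoint, has no event definition, and the written rules could let a death judged unrelated to tumour and drug be censored or replaced instead of counted as a failure

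*Combined protocol and SAP*

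**What the plan says.** Section 6.4 sets the endpoint: "The primary efficacy endpoint is progression free survival (PFS) at six months from patient registration for bevacizumab naïve patients", with PFS at 3 months for the bevacizumab-exposed group. Sections 1.1.1 and 3.1 repeat it. None of them says which events end PFS or how patients without an event are censored.

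Three neighbouring definitions are given:

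- **Progression (6.4.1.4.5)** covers imaging and clinical criteria. It brings in death only through "failure to return for evaluation due to death or deteriorating condition (unless clearly unrelated to this cancer".
- **Time to Treatment Failure (6.4.5)** ends at progression and several other events, including "death due to any cause, or early discontinuation of treatment". It is not listed as an endpoint in Section 1.1.
- **Time to Death (6.4.6)** runs "From date of registration to date of death due to any cause".

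Section 9 states "Time to progression and overall survival will be evaluated using the Kaplan-Meier product-limit survival curve methodology". The next sentence does name PFS: "Six-month Progression Free Survival (PFS) will be estimated using Kaplan-Meier estimates and associated two-sided 95% confidence intervals". The Group A decision rule is a count of patients: "If two or more patients are progression-free at 6 months (PFS6), an additional 25 patients will be accrued", and then "If 9 or more out of 34 have PFS6, then the study will be declared promising". Group B continues with at least 1 of 14 progression-free at 3 months and is promising with at least 2 of 32. Section 9 also counts patients who drop out for toxicity as failures, and replaces those who drop out for any reason other than progression or toxicity.

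**The concern.** The authors wrote any-cause death into two definitions and a restricted form of death into the one that feeds the primary endpoint. With no separate PFS definition, an analyst has to choose which applies.

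Consider a patient who dies, without documented progression, before the landmark and of a cause judged unrelated to both tumour and drug. Under 6.4.1.4.5 this is not progression. Under Section 9 it is not toxicity. If the death is treated as a drop-out, the patient is replaced and leaves the denominator of the Simon count. If the Kaplan-Meier analysis is run as time to progression, the patient is censored. Either way someone who did not survive to the landmark is not a failure, and the estimated PFS6 or PFS3 is too high. The go/no-go count could then depend on a cause-of-death judgement and on a rule settled after the data are known.

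**Working it through.** **Inputs from Section 9.** Group A: first stage 9, continue with ≥2; total 34, promising with ≥9; null 15%, alternative 35%. Group B: first stage 14, continue with ≥1; total 32, promising with ≥2; null 1%, alternative 12%. Both are stated as 5% error and 80% power.

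**Input not in the documents.** Let d be the share of patients who die before the landmark of a cause judged unrelated to tumour and drug, without progression. This is an assumption, taken over 2% to 10%. For scale, one patient is 1/34 = 2.9% of Group A and 1/32 = 3.1% of Group B.

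**Step 1: reproduce the design.** With n1 and c1 the first-stage size and threshold, and n and c the totals, the chance of declaring promise at a true rate p is

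P(p) = Σ over x from c1 to n1 of Bin(x; n1, p) × Pr[Bin(n − n1, p) ≥ c − x].

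- Group A: P(0.15) = 0.0474 and P(0.35) = 0.8107. The chance of stopping after stage 1 at the null is 0.5995.
- Group B: P(0.01) = 0.0287 and P(0.12) = 0.8010. The chance of stopping after stage 1 at the null is 0.8687.

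A search for the design with the smallest expected sample size under the null returns the same two designs. The stated 5% is a ceiling, and the attained errors lie below it.

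**Step 2: remove these deaths from the denominator.** Suppose the any-cause PFS rate equals the null p0. If a share d is taken out, the rate among those counted is p0/(1 − d). For Group A with d = 5% this is 0.15/0.95 = 0.1579. The formula is exact for replacement and stands in here as an approximation for censoring.

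| d | Group A apparent rate | Group A false promise | Group B apparent rate | Group B false promise |
|---|---|---|---|---|
| 0 | 0.1500 | 0.0474 | 0.0100 | 0.0287 |
| 2% | 0.1531 | 0.0528 | 0.0102 | 0.0298 |
| 3% | 0.1546 | 0.0558 | 0.0103 | 0.0304 |
| 5% | 0.1579 | 0.0622 | 0.0105 | 0.0315 |
| 10% | 0.1667 | 0.0818 | 0.0111 | 0.0348 |

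Group A passes the stated 5% already at d = 2%. Group B stays below 5% throughout.

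**Step 3: count these deaths as failures.** The rate stays at p0, so both designs keep the error and power found in Step 1.

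**The case against.** The strongest reply is that this is an unstated definition and not an exclusion. The endpoint is called progression-free survival throughout, and that name ordinarily includes death. Section 6.4.1.4.5 defines an objective status to be recorded at each evaluation, not a list of PFS events. Section 9 names PFS for the six-month Kaplan-Meier estimate directly after mentioning time to progression. No sentence says that a death is a drop-out, or that an unrelated death is censored or replaced. All of this stands, so the point is an ambiguity with a direction and not a demonstrated bias.

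The exposed group is also small. Toxicity drop-outs are already failures, so a treatment-related death would most naturally be one too. Thromboembolic events and sepsis are listed drug risks in Section 13. The exception needs a death that is clearly unrelated, so doubtful cases count as progression. Section 2.1.2 excludes several recent cardiovascular events and uncontrolled infection. This limits the likely size of d but does not settle how the remaining deaths are handled.

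It can also be said that local judgement over cause of death adds little, because clinical worsening is already a locally judged progression criterion. That is fair, and the point does not rest on it.

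What the reply does not answer is that a written exception for some deaths sits beside a written replacement rule, and nothing says that the endpoint's name overrides them.

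**Conclusion.** The point holds as a gap in the definition of the primary endpoint: the plan does not say how a death unrelated to tumour and drug enters the Simon count or the Kaplan-Meier estimate, and one literal reading removes it. If it is removed, the bias is upward. Its effect on the decision is modest in Group A (4.7% to between 5.3% and 6.2% for d of 2% to 5%, and 8.2% at 10%) and slight in Group B (2.9% to between 3.0% and 3.5%). These figures rest on the assumed d and on reading the null rates as any-cause PFS rates.

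Three stronger readings are not supported:

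- A reader might infer that the plan definitely makes such deaths non-events. It is silent on this.
- A reader might score such a patient as progression-free at the landmark. The apparent rate would then be p0 + d, and Group A's false-promise risk would be 11.8% at d = 3% and 18.8% at d = 5%. No text supports scoring a patient who has died as having PFS6.
- A reader might conclude that the trial's rates cannot be compared with the historical ones in Section 1.2.1 (9–15% PFS6; about 0% after bevacizumab failure). The protocol does not say how those sources treated deaths, so this cannot be judged.

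It should be fixed. Confidence is medium.

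**What to change.** In Section 6.4, add a definition: PFS is the time from registration to the first of progression under 6.4.1.4.5 or death from any cause, with explicit censoring rules. In 6.4.1.4.5, confine the exception for unrelated causes to deterioration or failure to return, so that it no longer applies to death. In Section 9, state for both groups that any death before the landmark is a failure in the Simon count, stays in the denominator and is not replaced, and make the time-to-progression wording agree with PFS.

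The cost is a few sentences. Survival follow-up is already planned (Sections 3.4.4 and 3.7.2). The sample sizes of 34 and 32 and all decision thresholds are unchanged. The only downside is that the reported PFS rate may be slightly lower.
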